## **5.0 Inclusion and Exclusion Criteria/ Study Population**

Inclusion criteria include: 1) age 18-41; 2) currently pregnant or postpartum; 3) if pregnant, receiving prenatal care; 4) English fluency; 5) owner of a cell phone with SMS text-message based capability; 6) access to WIFI and a device to allow audio and video teleconferencing; 7) able to provide informed consent. Exclusion criteria: None

## **6.0 Number of Subjects**

A total of 450 participants will be randomized in Specific Aim 1 (n=100) and Specific Aim 2 (n=350). To randomize 450 participants we will need to approach about 1,500 participants in order to get to 450 total participants.

## **7.0 Setting**

Recruitment will occur remotely, in person and via the EHR. Potential participants will be pregnant women receiving prenatal care and postpartum women.

## **8.0 Recruitment Methods**

Recruitment will occur remotely, in person and via the EHR. A Research Data Request will be submitted to obtain a recruitment report of MUSC patients who potentially meet eligibility criteria. The recruitment report will include a search for pregnant and postpartum women. The report will include mrn, age, race, ethnicity, date of prenatal care visit, date of postpartum visit, delivery date, ob/gyn provider name, MyChart account (Yes/No), cell phone number, email address and current ICD-9 or 10 diagnoses. The purpose of the ICD codes will be to ensure we are approaching enough women with substance use disorders, and/or a mood or anxiety disorder diagnoses, and therefore likely to screen positive on either an in-person or text-message SBIRT screening. In addition, ICD codes will be used for urn stratification at randomization. Any patients who have not opted out of being contacted for research will be contacted by phone call or text message and invited to participate. If a cell phone number is not available, the message with a link to a RedCap eligibility survey will be sent via email or MyChart message. The study team will not cold-contact any patients who have chosen to opt-out of receiving contact about research or who have met the maximum number of contact attempts at the time of recruitment. Our PI's clinic policy is to ask all patients if they would like to be contacted for research opportunities and if they prefer to be contacted by phone or text message. The vast majority of women prefer to be contacted through a text message. Therefore, we believe cold-contacting patients via text is acceptable for this study. All other patients will be contacted through their providers to be informed of the study if the provider feels it is appropriate. If the potential participant's provider has agreed to have the study team contact their patient, a phone call or text message will be sent to the potential participant inviting them to take part in the study. If a cell phone number is not available, the message with a link to a RedCap eligibility survey will be sent via email. If the potential participant does not respond to the phone call, text or email, the study team may also notify potential participants that a message was sent to them via MyChart. The text message (or email/MyChart message) will include a link to a brief RedCap eligibility survey. For those meeting the eligibility screening criteria, the RA/RC will schedule a time to verify eligibility criteria and review the informed consent either remotely or in-person.

Another method of recruitment will include Women's Health Services clinics, where after women are identified as pregnant or postpartum by the patient's nurse or provider, they will be approached by the study team, with the provider's permission, to take part in the study. Additionally, research staff may do a review of Women's Health Services provider schedules and patient charts in EPIC to identify potentially eligible women for inclusion. Research staff will approach patients when they arrive for their regularly scheduled appointment.

We will also recruit from the MUSC antepartum unit and the mother-baby unit. Patients will be approached by the study team, with the provider's permission, to take part in the study. Additionally, research staff may do a review of the antepartum and mother-baby unit schedules and patient charts in EPIC to identify potentially eligible women for inclusion. Research staff will approach patients while they are staying on the antepartum and mother-baby units. If the patient agrees to taking part in the study the RA will consent the participant and complete baseline procedures.

Another way to recruit is the potentially eligible patients in the PI and Co-Is practices will be informed and approached about the study as the PI and Co-Is feel is appropriate. Participants will also be recruited via study advertisement (e.g., flyers) and online postings (e.g., social media, linkedin).

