### ***Quality Assurance***

Accuracy and completeness of the data collected will be ensured by weekly review. The REDCap system does not accept outliers, illogical response patterns, etc. The PI and research assistants will have weekly meetings to discuss any qualitative comments received during data collection and any problems in data collection. The PI will examine the database for potential irregularities monthly. Initial data analyses will examine distributions of variable scores and comparability of baseline characteristics across conditions in case analyses need to be adjusted for these. Confidentiality procedures are outlined above.

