Statistical Analysis Plan

Sample Size and Power Analysis

Using a chi-square testing framework and a significance level of 0.05 and assuming two-sided hypothesis testing, both primary and secondary outcomes included a large enough sample size to detect differences between groups. Our a priori group sample sizes (usual care: n=191; LTWP: n=224) provided 80% power to detect between-group absolute differences in proportions ranging from 6% to 12% in the primary study outcomes (for example, screened: 65.2% [usual care] versus 77.7% [LTWP]; screened positive: 21.7% versus 34.2%, respectively; referred: 12.5% versus 23.1%, respectively; and attended treatment: 2.1% versus 8.3%, respectively). Our group sample sizes among participants completing a screen (usual care: n=63; LTWP: n=221) provided 80% power to detect between-group absolute differences in proportions ranging from 11% to 18% in the secondary study outcomes (for example, screened positive: 17.5% [usual care] versus 35.4% [LTWP]; referred: 3.2% versus 15.3%, respectively; and attended treatment: 1.6% versus 12.3%, respectively). The usual care rates used in these calculations were based on data published from earlier work on the LTWP program.

Data Analysis

We will assess the adequacy of randomization by comparing LTWP versus usual care (UC) on demographic, obstetric, and psychiatric baseline characteristics, using t-tests or Wilcoxon rank sum tests for continuous variables and chi-square tests or Fisher's exact tests for categorical variables, respectively. Descriptive statistics will be calculated for each screening method (LTWP versus usual care), including counts and percentages for participants who were screened, screened positive, referred to treatment, and attended treatment. Unadjusted differences in outcomes between people assigned to LTWP versus UC will be calculated using chi-square tests because all study outcomes are dichotomous. Relative risk (RR) ratios will be estimated and reported along with their 95% confidence intervals. All hypothesis tests will be two-sided with a type 1 error set at 0.05, and all analyses will be performed using SAS statistical software, version 9.4 (Cary, NC).

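### Randomisation is stratified by ICD diagnosis but the SAP tests every outcome unadjusted; the cost is efficiency against a stratified analysis, and it is small for treatment attendance

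*Protocol*

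**What the plan says.** On the design side, protocol section 8.0 (Recruitment Methods) says: "In addition, ICD codes will be used for urn stratification at randomization". The same paragraph explains why the codes are collected: women with substance use, mood or anxiety diagnoses are "therefore likely to screen positive on either an in-person or text-message SBIRT screening". Neither document defines the diagnosis groups, their number or the urn parameters.

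On the analysis side, the SAP (Data Analysis) says: "Unadjusted differences in outcomes between people assigned to LTWP versus UC will be calculated using chi-square tests because all study outcomes are dichotomous". It adds: "Relative risk (RR) ratios will be estimated and reported along with their 95% confidence intervals". It does not mention the urn, a stratum or a covariate. That the relative risk is a crude one is an inference, but a fair one, since no model or stratified estimator is named.

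The only opening for adjustment is in protocol section 12.0 (Quality Assurance), where initial analyses look at "comparability of baseline characteristics across conditions in case analyses need to be adjusted for these". That depends on what is observed, does not name the ICD factor, and is not carried into the SAP.

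**The concern.** A factor that is used to balance the arms and that predicts the outcome normally belongs in the analysis. If it is left out, one of two things happens. When the balancing is tight, variation between diagnosis groups no longer contributes to the real variability of the arm difference, yet the pooled chi-square variance still counts it. The test is then conservative and the intervals slightly wide. When the balancing is loose, that variation stays in the estimate as noise that stratification would remove. Either way the trial gets less from its data than it could.

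The SAP's reason for the unadjusted test, that the outcomes are dichotomous, is no reason to drop the stratifier: Mantel-Haenszel methods are made for binary outcomes. Leaving the matter to an imbalance check also makes adjustment a decision taken after seeing data.

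**Working it through.** **Inputs from the SAP.** Two-sided 0.05; usual care 191, LTWP 224. Usual care versus LTWP: screened 65.2% vs 77.7%; screened positive 21.7% vs 34.2%; referred 12.5% vs 23.1%; attended 2.1% vs 8.3%. Secondary outcomes use 63 and 221.

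**Inputs assumed, because the documents give none.** One binary ICD stratum holding 20%, 35% or 50% of women, and a stratum-outcome odds ratio (OR) of 2, 4 or 8.

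**Step 1: the plan's own power.** Power = Φ[(|p1 − p0| − 1.96·s0)/s1], where s0 = √[p̄(1 − p̄)(1/n0 + 1/n1)] and s1 = √[p0(1 − p0)/n0 + p1(1 − p1)/n1]. For screened positive:

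- p̄ = (191 × 0.217 + 224 × 0.342)/415 = 0.2845
- s0 = 0.0444, s1 = 0.0435
- power = Φ[(0.125 − 1.96 × 0.0444)/0.0435] = Φ(0.87) = 80.8%

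All seven SAP rate pairs give 80.2% to 80.8%. The stated 80% reproduces, and it belongs to the unadjusted test.

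**Step 2: why tight balance makes the unadjusted test conservative.** The pooled variance splits as p̄(1 − p̄) = Σπk·pk(1 − pk) + Σπk(pk − p̄)². With exact balance only the first part is real. Take screened positive under the null at 21.7%, 35% diagnosed, OR 8. The stratum rates are then 44.9% and 9.2%.

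- total variance: 0.217 × 0.783 = 0.1699
- between strata: 0.35 × 0.65 × (0.4486 − 0.0923)² = 0.0289
- real share: (0.1699 − 0.0289)/0.1699 = 0.83
- true size: 2[1 − Φ(1.96/√0.83)] = 2[1 − Φ(2.15)] = about 3.1%

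Simulation gives 2.9%, in agreement.

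**Step 3: power, unadjusted against stratified.** 40,000 simulated trials per scenario, each analysed with Pearson's chi-square and with the Cochran-Mantel-Haenszel (CMH) statistic, [Σ(ak − n1k·mk/Nk)]² / Σ{n1k·n0k·mk(Nk − mk)/[Nk²(Nk − 1)]}, both against 3.84. Monte Carlo error of one power figure is about √(0.8 × 0.2/40,000) = 0.2 points. Exact balance, 35% diagnosed; power of chi-square → CMH, %:

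| Outcome | OR 2 | OR 4 | OR 8 |
|---|---|---|---|
| Screened | 81.3 → 81.8 | 81.2 → 83.0 | 82.0 → 85.2 |
| Screened positive | 81.0 → 81.7 | 81.8 → 84.6 | 82.9 → 88.6 |
| Referred | 80.9 → 81.4 | 81.6 → 83.8 | 82.1 → 86.4 |
| Attended | 83.4 → 83.5 | 83.4 → 84.0 | 83.6 → 84.9 |

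At 50% diagnosed the picture is similar (screened at OR 8: 82.7 → 87.1). At 20% the gains under exact balance are mostly smaller (screened at OR 8: 82.4 → 83.4). At OR 1 nothing changes.

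**Step 4: no balancing at all.** An urn lies between exact balance and none, so the runs were repeated with none. The size of the chi-square for the three commoner outcomes returns to about 5%, but the power gap stays or widens. Over 35% and 50% diagnosed, with and without balance, the gains for those outcomes are about 0.5 to 1 point at OR 2, 2 to 3 at OR 4 and 3 to 7 at OR 8. For attendance they are 0 to 1.6 points. At 20% diagnosed, OR 8 and no balancing, a rerun gave about 2 points for attendance, so that gain stays small.

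**Step 5: size and intervals.** Under exact balance the chi-square's size for the commoner outcomes runs from nearly 5% at OR 2 to about 2.9% at OR 8, while CMH stays near 5%. For attendance both tests sit at about 4% because events are sparse. For screened positive the crude standard error of log RR is √[0.658/(224 × 0.342) + 0.783/(191 × 0.217)] = 0.166. The Mantel-Haenszel value falls to 0.151 at OR 8, 9% smaller. For attendance the largest reduction is about 2% (0.547 to 0.536). Coverage of the crude interval is about 95% to 97%.

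**The case against.** The strongest reply is that the unadjusted test remains a valid analysis that delivers what the SAP promises. "Our a priori group sample sizes (usual care: n=191; LTWP: n=224) provided 80% power" refers to this very test, the figure reproduces, and simulated power stays at or above 80% in every scenario. That stands.

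Three stronger readings are tempting, and the documents do not support them.

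- A reader might infer that planned power is lost or the trial underpowered. It is not; the loss exists only relative to a stratified analysis.
- A reader might infer that ignoring the urn inflates false positives, or that chance imbalance in diagnosed women is mistaken for effect. The size is at or below about 5% throughout, and chance imbalance is already inside that error rate. Tight balance gives a conservative test and loose balance a roughly nominal one; the two drawbacks do not occur in full together.
- A reader might infer a large gain. With stratum rates of 40% and 3.4% and half of women diagnosed, power for screened positive goes from 84% to 91%, but the odds ratio there is (0.40/0.60)/(0.034/0.966) = 19, and nothing in the documents supports a stratifier that strong.

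It is also fair that the protocol links diagnosis only to screening positive, not to completing a screen or attending treatment, and that the gain is least for the Aim 2 primary outcome.

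The baseline check under Quality Assurance is a partial answer at best: it is contingent and does not name the stratifier. The mismatch itself is not disputed.

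**Conclusion.** The point holds as a matter of efficiency and of matching analysis to design. It is not a threat to validity. Under the assumed odds ratios of 2 to 8 and 35% or 50% of women diagnosed, the SAP forgoes about 0.5 to 7 points of power for screened, screened positive and referred, and 0 to 1.6 points for attended treatment. If the urn balances tightly, the unadjusted test also runs at about 3% to 5% and its intervals are slightly wide. If it balances loosely, size is about 5% and the power gap remains.

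That the mismatch exists is certain from the text. Its size is not, because the documents give neither the prevalence of the ICD groups nor their strength. For the secondary outcomes among women who completed a screen, urn balance is not assured and no gain has been shown. The change of allocation ratio in Aim 2 is a separate matter and is not part of these figures.

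**What to change.** In the SAP's Data Analysis section, for the outcomes compared across all randomised women:

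- Make a CMH test the primary analysis, with the Mantel-Haenszel relative risk and risk difference and their 95% confidence intervals.
- Stratify by the urn's ICD groups exactly as used at randomisation, including whatever level the urn gave to women without an ICD record. The protocol also recruits by flyer and online posting, so the SAP should state that level.
- Write down the groups and keep them few. Only about 0.021 × 191 = 4 usual-care attenders are expected.
- Keep the unadjusted chi-square and relative risk as a sensitivity analysis.
- The same stratified analysis may be used for the screen-completer outcomes, without claiming a gain there.

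The cost is low. The factor must already be recorded to run the urn, and SAS, which the SAP already names, offers the method. There are two small drawbacks: the strata have to be defined in writing, and stratified estimates for attendance will rest on sparse cells.

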## **9.0 Consent Process**

Signed informed consent will be obtained from study participants. The consent process will take place via one of the following modalities: 1) Remote or in person electronic consent (e-consent) via REDCap (if remote, e-consent will be facilitated with a discussion over the phone or via video), 2) Remote consent via doxy.me facilitated with either a discussion over the phone or video connection via doxy.me, 3) Mailed (paper) consent facilitated with a discussion over the phone, or 4) in person consent (e.g., in clinic).

All participants will be provided with a hard copy and/or an electronic copy of the consent form. Participants will be informed that participation in this research is strictly voluntary. Informed consent will include a detailed description of the purpose and the procedures of the study emphasizing our policy regarding privacy and confidentiality and an opportunity for the individual to ask any questions or voice concerns. Signatures on the consent form may be obtained with paper and pen OR electronically via REDCap or doxy.me. Participants who do not have access to the required technology to complete consent remotely via REDCap or doxy.me will be given the option to complete consent via mail facilitated with a discussion over the phone.

## **10.0 Study Design / Methods**

Specific aim 1: A two arm pilot RCT (N=100) with 2:1 allocation will examine feasibility and preliminary efficacy of LTW, compared to TAU. Specific aim 2: A RCT (N=350) with 2:1 allocation will examine effectiveness of LTW, compared to TAU. As of the approval of amendment #12 the allocation will switch to 1(LTW):2(TAU) for specific aim 2. Recruitment will primarily occur proactively and remotely via the EHR. We will conduct a weekly EHR search via a recruitment report for all new pregnant and postpartum patients in the past week. The report will include mrn, age, race, ethnicity, date of prenatal care visit, date of postpartum visit, delivery date, ob/gyn provider name, MyChart account (Yes/No), cell phone number, email address and current ICD-9 or 10 diagnoses. Any patients who have not opted out of being contacted for research will be contacted and invited to participate. The study team will not cold-contact any patients who have chosen to opt-out of receiving contact about research or who have met the maximum number of contact attempts at the time of recruitment. If the potential participant has not opted out of being contacted, or the potential participant's provider has agreed to have the study team contact their patient, a phone call will be made or message will be sent via text, email or MyChart message to the potential participant inviting them to take part in the study. This invitation will include clear opt out procedures should the patient not wish to be contacted in the future for the purpose of this study. If interested, participants will complete a screening online via REDCap to determine study eligibility (see above for inclusion criteria). After completing preliminary determination of eligibility, if eligible and interested in participating in the study, participants will be scheduled for a time to complete informed consent (see 9.0 Consent Process).

Following consent, all participants will subsequently be text messaged and/or emailed a REDCap link, accessible via smartphone, tablet, or computer to complete study assessments. Assessments that need to be completed by interview will be scheduled with study staff and completed via doxy.me or telephone. For specific aim 1 participants only, participants will also complete voice analysis through Surveylex. Participants will be presented with a questionnaire consisting of one task to complete through the Surveylex online form. One task to be answered and entered as text, and three tasks involving voice recordings in response to prompts. The tasks in the online form include the following: Text question (one task): 1) What is your participant ID?; Voice recording (three tasks): During voice recording tasks, the participant will be reminded that there is no right or

wrong answer for these tasks and that they may choose to skip the question or stop their answer at any time 1) Please repeat this phrase: "The quick brown fox jumped over the lazy dogs." (10 seconds) 2) Please describe yesterday from start to finish (30 seconds) and 3) Please describe what brings you happiness (30 seconds). Assessments will occur at baseline (following consent). Participants will be randomized to LTW or TAU, respectively.

Survey assessments are estimated to take 30 minutes to complete and will be administered remotely via REDCap through our established procedures and via doxy.me or telephone for interview assessments. Voice analysis for specific aim 1 participants only takes less than 10 minutes to complete and can be completed remotely. Participants will be compensated via electronic gift cards which will be emailed or texted to participants. Participants will receive \$25 for completion of the baseline assessments. To encourage participants to complete all 3 surveys, participants will be paid an additional \$20 if they complete all 3 surveys (baseline).

Assessments include

Measures	Baseline
Consent	X
Randomization	X
Demographics Questionnaire	X
EPDS Survey	X
NIDA Modified Assist	X
Accountable Health Communities (AHC) Health-Related Social Needs (HRSN) Screening Tool	X
The Medical Outcomes Study Short Form Survey 36 (SF-36v2)	X
*Voice Biomarkers	X
**GAD-7 Anxiety	X
***Columbia Suicide Severity Rating Scale (CSSRS)	X
***Timeline Follow-Back (TLFB)	X
***Usability Scale Survey	X

\*Only the 100 participants in specific aim 1 complete voice biomarkers

\*\*Only participants in specific aim 2 complete the GAD-7, CSSRS and TLFB

\*\*\*Only participants assigned to LTW will complete the usability scale

+ As of the approval of amendment 10 newly enrolled participants will not complete CSSRS and TLFB. Participants consented prior to the approval of amendment 10 will complete CSSRS and TLFB at baseline.

Specific aim 3: We will gather healthcare utilization data on our study participants who have Medicaid insurance. The MUSC study team will extract the maternal Medicaid IDs from our study participants with Medicaid insurance from the EHR. We will share a list of these maternal Medicaid IDs with Medicaid, and they will return data related to maternal and newborn diagnosis codes, health care utilization and costs for these participants i.e., prenatal care visits, postpartum care visits, hospitalizations and ED visits during pregnancy and the postpartum year. The MUSC study team will send the maternal Medicaid ID's of study participants to Medicaid in a password protected spreadsheet. Medicaid will send the MUSC study team a password protected spreadsheet of data. The spreadsheet of data Medicaid will send back to MUSC will be coded since

it will contain the Medicaid ID's of participants.

The Medicaid ID is the only link to subjects in the study. The document linking Medicaid ID's and our study participants will be stored on a University secure network drive or in MUSC BOX. The linking document will be stored separately from the study data and only trained study personnel will have access to the linking document.

Study data will be stored on a University secure network drive or in MUSC BOX. The spreadsheet of data that Medicaid will send the MUSC study team will be password protected. Only trained study personnel will have access to the password protected data spreadsheet.

The MUSC study team will have access to the Medicaid ID's as well as Medicaid.

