## 1.0 Objectives / Specific Aims

### Specific Aim 1

The goal of Specific Aim 1 is to develop an effective remote mental health and substance use Screening, Brief Intervention and Referral to Treatment (SBIRT) program for pregnant and postpartum women. The **objectives** of this current application for Specific Aim 1 are to conduct a pilot RCT of a text-message based SBIRT and home-based telemedicine services for pregnant and postpartum women – called Listening to Women (LTW), compared to treatment as usual (TAU) with the primary objective to provide effect size estimates for a larger RCT.

**Specific Aim 1:** Conduct a pilot, small-scale randomized controlled trial to examine feasibility and preliminary efficacy of LTW, compared to TAU. Outcomes related to feasibility include percentage of eligible patients recruited, **study attrition**, **study retention**, and mental health and substance use treatment appointment attendance. Outcomes related to **preliminary efficacy** will include participation in screening, referral and treatment at baseline, compared to TAU.

The central hypotheses for Specific Aim 1 are that the study is feasible and women assigned to LTW will be more likely to screen positive and successfully obtain treatment in less time, compared to those that are assigned to TAU.

### Specific Aim 2

Upon completion of Specific Aim 1, the goal of Specific Aim 2 is to evaluate the effectiveness of a remote mental health and substance use Screening, Brief Intervention and Referral to Treatment (SBIRT) program for pregnant and postpartum women. The **objectives** of this current application for Specific Aim 2 are to conduct an RCT of a text-message based SBIRT and home-based telemedicine services for pregnant and postpartum women – called Listening to Women (LTW), compared to treatment as usual (TAU) with the primary objective to include attendance to treatment at baseline, compared to TAU.

**Specific Aim 2:** Conduct a randomized controlled trial to examine the effectiveness of LTW, compared to TAU. Outcomes related to **effectiveness** include attendance to treatment at baseline, compared to TAU.

The central hypotheses are that a greater proportion of women assigned to LTW will attend treatment following a referral, compared to TAU.

### Specific Aim 3

The goal of Specific Aim 3 is to gather data related to maternal and newborn diagnosis codes, health care utilization, and costs for our study participants with Medicaid.

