To address these barriers we designed, implemented and piloted LTW in routine perinatal care in one obstetric practice (see 3.0 Intervention to be Studied) as part of a quality improvement project. Our pilot demonstrates high rates of participation with 87.78% (273/311) of women approached agreeing to take part in LTW and completing the text-message screening. Preliminary data comparing LTW (N=273) to a historical dataset extracted from the EHR including peripartum women receiving in-person SBIRT in the same clinic (N=2,988) found a significantly greater proportion of women enrolled in LTW screened positive (81.15% vs. 33.33%;  $\chi^2=169.50$ ,  $p<0.0001$ ), were referred for treatment (76.12% vs. 57.63%;  $\chi^2=18.03$ ,  $p<0.0001$ ), and received treatment (94.91% vs. 16.04%;  $\chi^2=245.41$ ,  $p<0.0001$ ), compared to women receiving in-person SBIRT.

While these preliminary data are exciting, a randomized control trial will be necessary to determine the feasibility and efficacy of LTW. The goal of Specific Aim 1 is to examine the feasibility and preliminary efficacy of the proposed RCT methodology. Specific Aim 1 will inform Specific Aim 2 to then conduct a larger-scale RCT that examines LTW, compared to a control condition. This will allow us to identify and address barriers in recruitment, retention, use of LTW, and other procedures essential to successful conduct of the RCT. This approach is consistent with expert recommendations to use pilot mechanisms to test the feasibility of doing a full-scale RCT, use data yielded by the pilot study to “de-bug” the methodology, and to assess optimal strategies to executing the RCT [51- R34].

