**Secondary pilot feasibility and acceptability outcome variables include:**

Recruitment: We will determine the proportion of patients who agree to participate as compared to the total number solicited to enroll for each recruitment approach.

Attrition: We will examine the proportion of study participants that prematurely terminate i.e., do not complete screenings, or are unable to be contacted for referral and/or treatment.

Study retention: We will determine the proportion of study participants that complete all assessment points associated with the protocol.

Treatment Attendance: We will collect data from the EHR to determine the proportion of participants that attended a mental health or substance use treatment appointment.

Improved Health-Related Social Needs: Among women referred for treatment, we will compare the change in health-related social needs measured by the Accountable Health Communities (AHC) Health-Related Social Needs (HRSN) Screening Tool among those assigned to LTW, compared to TAU.

Voice Biomarkers: Voice analysis will be completed using an online platform SurveyLex (owned by NeuroLex, Inc.). Among women referred for treatment, we will analyze voice recordings for characteristics (acoustic, linguistic, or meta feature) which may be compared between those assigned to LTW and those assigned to TAU, and compared to other measures collected in either LTW or TAU including EPDS, NIDA Modified Assist, and/or AHC HRSN.

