#### **Protections Against Loss of Confidentiality**

All screening information will be kept in a password protected REDCap database. Only key study personnel will have access to the database. If an individual is not eligible to participate based on her answers to the eligibility survey, her screener will not include her name or contact information. Only people who meet eligibility criteria based on the answers to the eligibility survey will be asked if they would like to be contacted about participation in the study and for their name and contact information. Eligible participants' full name, telephone number and

e-mail address will be recorded in the study enrollment log located on a secure MUSC drive or in MUSC Box. The REDCap database and the study enrollment log are the only places where participants' names and subject identification numbers appear together. Eligible participants will be assigned a subject number, will complete informed consent, will be randomized, will complete baseline assessments, and subsequently will receive their randomized intervention.

Upon completing eligibility screening, if study eligible, individuals will be provided with an overview of the study, asked to review study procedures via a consent form, and asked to provide signed consent. Participants will be informed of limitations of confidentiality (i.e., abuse or neglect, intention to harm self or someone else) both verbally and/or in writing during the informed consent process. The consent form will include the participant's name, but not his/her subject number. Consent forms will be provided in English.

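### As written, the LTW-only usability scale is given at baseline, before women receive LTW, and no later administration is scheduled

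*Protocol*

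**What the plan says.** The assessment table in Protocol section 10.0 has one time column, headed Baseline. The row "Usability Scale Survey" has its only mark there. The footnote below the table limits who answers: "Only participants assigned to LTW will complete the usability scale". It does not say when, and it does not restrict the scale to one aim.

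The timing comes from two other places. The text of section 10.0 states "Assessments will occur at baseline (following consent") and names no later assessment. Section 13.0, under Protections Against Loss of Confidentiality, says that eligible women consent and then "will be randomized, will complete baseline assessments, and subsequently will receive their randomized intervention".

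Protocol section 2.0 says that the pilot is meant to help the team "identify and address barriers in recruitment, retention, use of LTW, and other procedures essential to successful conduct of the RCT". Section 4.0 has a list under the heading "Secondary pilot feasibility and acceptability outcome variables include"; its items are recruitment, attrition, retention, treatment attendance, social needs and voice biomarkers. Usability is not among them. The SAP does not mention the scale.

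**The concern.** A usability scale asks users about something they have used. Section 3.0 describes what LTW consists of: screening by text message, automated feedback, contact with a care coordinator and, where appropriate, a telemedicine visit at home. On the section 13.0 order, a woman answering at baseline has met none of these. Her answers can reflect only what she expects of the program, or her impression of the link used for the research questionnaires. No analysis can recover the missing experience afterwards.

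At stake is what the pilot can tell the team about use of LTW from the woman's side. No other instrument in the assessment table asks for this. Attendance and attrition can show that women dropped out, but not whether the text screening or the remote contact was hard to use.

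**Working it through.** There is no stated figure to reproduce. The check sets the passages side by side and then counts the women concerned.

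**Order of events**

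| Source | Order given | Consequence for an LTW-only scale at baseline |
|---|---|---|
| Protocol 13.0, Protections Against Loss of Confidentiality | Consent, randomization, baseline assessments, intervention | Can be assigned, but precedes the program it rates |
| Protocol 10.0, running text | Consent and baseline assessments, with randomization mentioned afterwards | Cannot be assigned, because the arm is not yet known |

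Neither order gives a score that reflects use of LTW.

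**Count from the schedule**

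- Scheduled time points: 1 (Baseline).
- Administrations of the scale after LTW exposure: 0.
- Other user-reported usability or satisfaction instruments in the table, the endpoints (section 4.0) or the SAP: 0.

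**Women affected, if the footnote applies to both aims**

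Inputs: Aim 1 N = 100 and Aim 2 N = 350 (sections 6.0 and 10.0). Aim 1 allocation is 2:1, LTW to usual care. Aim 2 starts at 2:1 and changes to 1:2 when amendment 12 is approved (section 10.0).

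- Aim 1: 100 × 2/3 = 66.7, about 67 women.
- Aim 2: let m be the number randomized before the change. The LTW arm is then (2/3)m + (1/3)(350 − m) = (350 + m)/3.
  - m = 0: 350/3 = 116.7, about 117 women.
  - m = 350: 700/3 = 233.3, about 233 women.
- Both aims: 67 + 117 = 184 to 67 + 233 = 300 women.

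The documents do not give m, so only the range can be stated. The SAP's LTW group of 224 lies inside 184 to 300. However, the SAP groups total 224 + 191 = 415 rather than 450, and the SAP does not say whether Aim 1 women are included, so it is not used to narrow the range.

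**The case against.** The strongest reply is that the word baseline is used loosely. Section 1.0 speaks of "attendance to treatment at baseline, compared to TAU", which is an event after assignment, and the Baseline column also holds consent and randomization. Section 3.0 has the text screening sent to women who agree to take part, with immediate feedback, so it could fall close to the baseline link. The table itself has faults. The three-asterisk marker also sits on the CSSRS and TLFB, which the two-asterisk footnote covers. The extra payment is due "if they complete all 3 surveys (baseline"), which may be a remnant of follow-up surveys since removed, though the documents do not confirm that.

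Much of this stands. A reader might infer that no woman had used any part of LTW when she answered. The documents do not establish that: it is certain only on the literal section 13.0 order, and practice may differ. But no passage places the scale after the text screening, and the only explicit sequence says the reverse. Even a scale sent just after the text screening would come before the care coordinator and the telemedicine visit for women who go on to them.

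A second reply is that usability is not an endpoint. That is correct. A reader might infer that the pilot's promised acceptability outcomes are lost, but section 4.0 spells out its feasibility and acceptability items without this scale, and all of them are independent of its timing. Nor do the documents support saying that a good score would be misread, since they give no plan for reporting it.

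A third reply is that a single Baseline column is the wider problem, because it also leaves the change-from-baseline endpoints in section 4.0 without a second measurement. That may be so, but adding later columns would repair this item only if the usability row is moved into one of them.

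**Conclusion.** The point holds for the schedule as written. The LTW-only usability scale precedes the program under section 13.0 and cannot be assigned under the order suggested by section 10.0, and nothing later is scheduled. It is the only user-reported usability instrument, so as scheduled it cannot serve the section 2.0 purpose of identifying barriers to use of LTW.

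The size is about 67 women in Aim 1 and between about 117 and 233 in Aim 2. This assumes that the footnote covers both aims, that enrolment reaches the planned numbers, and that the allocation ratios are met. The effect is confined to the usability evidence: no listed endpoint, no SAP analysis and not the primary attendance outcome depends on it. The change should be made, but it does not threaten the trial's main comparison.

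**What to change.** 1. Move the Usability Scale Survey out of the Baseline column to one defined time point after LTW exposure, at the earliest after the text screening and automated feedback. Send it by REDCap link to the LTW arm.
2. Report non-response, and which LTW components each woman had used when she answered.
3. Label any scores already collected before exposure as pre-use expectations, and do not pool them with later scores.
4. Reconcile the order of randomization, assessments and intervention between sections 10.0 and 13.0, and state whether the scale applies to both aims. If the scale is in practice already sent after exposure, correct the table to say so.

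The cost is one more column in the schedule, one automated survey in one arm and one extra contact, on a platform already in use. Some women will not answer. Section 10.0 pays only for baseline completion, so the team would also need to decide whether to compensate the later survey. Separate triggers by screening result, or a particular fallback date, are possible refinements, but the documents give no basis for requiring them.
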